Overview of imaging protocol: Prior to catheter angiography, the diagnostic evaluations of subjects entered into this protocol will not vary from that used on others who are not eligible or who do not wish to participate in the study. Subjects entered into the study, will because of their participation, undergo only two additional DSA imaging acquisitions. These will be done in conjunction with their standard diagnostic DSA evaluation and consist of two CBCTPs, one before and one after administration of 1 g acetazolamide through a peripheral IV line. Each CBCTP will require administration of 75-100 mL iodinated contrast medium also through an IV line. Neither of these imaging studies will be used for clinical decision making, but would be processed and evaluated at later date for a formal analysis of the results. Following completion of diagnostic imaging subjects will receive the usual standard of care for treatment of their ruptured aneurysm i.e. endovascular embolization or open surgical clipping.

Details of experimental imaging: An initial CBCTP acquisition will be done in conjunction with injection of iodinated contrast medium through a peripheral IV (75-100 mL iopamidol, Isovue 370; Bracco Diagnostics, Princeton, NJ). An IV is placed for normal standard-of-care for this disease process. After this 1 g of acetazolamide will be given through the IV line. Following a 20-minute delay a second CBCTP acquisition will be completed again in conjunction with injection of iodinated contrast medium at a dose identical to that used for the first CBCTP acquisition. Each of the CBCTP acquisitions take less than 2 minutes so, except for the 20-minute period following administration of the acetazolamide there will be no delay in the subjects' diagnosis or treatment.

Contrast: C-arm CBCTP will be performed with intravenous injection of contrast dye (iopamidol, Isovue 370; Bracco Diagnostics, Princeton, NJ) at a rate of 4 mL/s and a maximum dose range of 75-100 mL. The contrast bolus may be followed by a 50-mL saline push at a rate of 4 mL/s. The delay will be calculated from the conventional CTA/CTP that was performed prior. The contrast administered during the conventional CTA head and neck with perfusion performed prior will be 120 mL. Therefore, the maximum amount of IV contrast media that would be administered

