With our initial 10 patients we are able to report that in all 10 patients the images were successfully required. We then performed an analysis of the 20 total cerebral hemispheres (right and left). Nineteen of 20 hemispheres demonstrated a significant change in CBF perfusion in response to Diamox ($p<0.05$). Six hemispheres demonstrated a 30% change in CBF and 12 had a 15% change. In 9 hemispheres there was the expected increase in CBF in response to Diamox. In 10 hemispheres there was a decrease in CBF. There was no statistical difference in the percent change between left and right hemispheres which would correlate with the global vasodilatory effects of Diamox. Symptomatic vasospasm then only developed in 2 of our patients. In one of these patients there was a pathological decrease in CBF in response to Diamox while the other had an appropriate increase in CBF. The goal of the analysis in this extension of the study is to better understand the changes in CBF in patients that go on to develop symptomatic or clinical vasospasm based on a change in neurological exam. Unfortunately, in our first phase of the pilot study only 2 patients developed symptomatic vasospasm. The reason we are requesting an extension to 30 patients is so we can capture a

larger number of patients with symptomatic vasospasm. Then we can assess our statistical analysis to see if we can consistently see a significant lack of response (either <30% increase in CBF or a decrease in CBF) to Diamox. With only 2 patients in our initial cohort developing symptomatic vasospasm it is impossible to make a more robust statistical proposal and that is why we are submitting a request to study more cases.

As discussed before, in this study design there is no need for a control group. We are comparing our CBCT information to the conventional method which is the clinical neurological exam change which indicates clinical or symptomatic vasospasm. The data that will be statistically compared is the pre-diamox perfusion in comparison to the post-diamox perfusion. A statistically significant change increase in CBF represents an appropriate response to Diamox. Lack of change in CBF or decrease in CBF could be suggestive of potential for developing vasospasm. More data with patients who develop clinical vasospasm is needed in order to correlate these changes with this subset of patients.

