The statistics that will be performed on the data maps are outlined in the images below. Using the perfusion map values, we will calculate relative percent change or improvement factor which is detailed in the slides below. When we say the results were reproducible it means that we were able to detect a change in perfusion in response to Diamox and that the maps were of good enough quality to be diagnostic. I have included examples below.

The statistical analysis on the relative percent change in CBF was a standard basic paired t-test. This test was performed in an identical manner for each hemisphere for each perfusion parameter map. For a given hemisphere and map test here were 40 slices of the image above the orbital line, a mean measurement was made for each slice location of the hemisphere. Thus, for pre and post Diamox we obtained 40 paired samples. From these paired samples (paired meaning they shared the same slice location pre and post Diamox) the paired-test was performed by taking the difference between all of the pre and post paired samples to obtain a set of 40 differences. From these 40 difference values one can get a mean and standard deviation to obtain the T statistic where a corresponding p-value can then be calculated. For our data set, we are selecting p-value of <0.05 as significant. We do not plan to use this data for a power analysis. Reproducibility has been established, but we are now aiming to draw correlations between patients with vasospasm and their CBF response to Diamox and that is the main aim of this expanded portion of the study.

References

3. Lee, K., et al. "Triple-H' Therapy for Cerebral Vasospasm Following Subarachnoid Hemorrhage." *Neurocritical Care*, vol. 4, no. 1, 2006, pp. 68-76.

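### The per-hemisphere t-test counts 40 slices of one scan pair as 40 independent samples, so its p<0.05 cannot label a hemisphere as changed or as an appropriate response

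*Combined protocol and SAP*

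**What the plan says.** Under Scan procedure, the study imaging is "two CBCTPs, one before and one after administration of 1 g acetazolamide through a peripheral IV line". No repeat scan is planned in either condition.

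The last paragraph under IRB Concerns describes the test. For each hemisphere and each perfusion map, a mean is taken at each of 40 slice locations: "Thus, for pre and post Diamox we obtained 40 paired samples". The mean and standard deviation of the 40 differences give the t statistic, and p<0.05 is called significant. The readable text makes no allowance for correlation between slices.

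The same section uses this significance in three ways:

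- Pilot result: "Nineteen of 20 hemispheres demonstrated a significant change in CBF perfusion in response to Diamox".
- Meaning of reproducible: "When we say the results were reproducible it means that we were able to detect a change in perfusion in response to Diamox", together with maps of diagnostic quality.
- Planned analysis: "The data that will be statistically compared is the pre-diamox perfusion in comparison to the post-diamox perfusion", followed directly by "A statistically significant change increase in CBF represents an appropriate response to Diamox".

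It also gives a second criterion that does not use the t-test: "a significant lack of response (either <30% increase in CBF or a decrease in CBF) to Diamox".

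On effect sizes the pilot reports: "Six hemispheres demonstrated a 30% change in CBF and 12 had a 15% change". Nine hemispheres had an increase and ten a decrease.

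**The concern.** A paired t-test divides the mean difference by SD/√n, and this is the right standard error only if the n differences are uncorrelated. Here they are 40 parts of one brain, imaged once before and once after the drug. The slices share the contrast injection, the reconstruction and the patient's physiological state at each scan, so positive correlation is to be expected.

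Two things go wrong. Correlation between neighbouring slices makes the effective sample size smaller than 40. In addition, any shift that affects a whole scan moves all 40 differences together. Such a shift enters the mean but not the SD, so the test cannot tell it from a drug effect.

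At stake is whether a significant result says anything about a single hemisphere. If the false-positive rate is well above 5%, a hemisphere with no real response can be recorded as an appropriate responder, and the pilot count cannot be read at its stated level. The second definition of response adds to the problem, because it can put the same hemisphere in the opposite class.

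**Working it through.** **Inputs from the document.** 40 slice differences per hemisphere, ordinary paired t-test, p<0.05 (IRB Concerns); one scan before and one after (Scan procedure); 20 pilot hemispheres, of which 19 significant, 9 increased, 10 decreased and 6 with a 30% change (IRB Concerns). The test is taken as two-sided, because both increases and decreases are reported.

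**What can be reproduced.** 9 + 10 = 19, which matches the number of significant hemispheres. No slice values or SDs are given, so the 19 p-values cannot be recomputed.

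**Threshold.** With n = 40 there are 39 degrees of freedom and the critical |t| is 2.0227. A hemisphere is significant when |mean|/SD exceeds 2.0227/√40 = 0.32. With independent differences the simulated error rate is 5.0%, as intended.

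**Neighbour correlation (assumed).** Slice differences follow an AR(1) process with correlation ρ and no true change; 200,000 simulated hemispheres per row. Effective n = 40 / [1 + 2 Σ(1 − k/40)ρ^k], with k from 1 to 39.

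| ρ | effective n | called significant | called a significant increase |
|---|---|---|---|
| 0 | 40 | 5.0% | 2.5% |
| 0.1 | 32.9 | 7.5% | 3.7% |
| 0.3 | 21.9 | 15% | 7.4% |
| 0.5 | 13.8 | 26% | 13% |
| 0.8 | 5.0 | 53% | 26% |
| 0.9 | 2.7 | 68% | 34% |

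**Correlation common to all slices (assumed), for example from a whole-scan shift.** The exact rate is 2·P(t39 > 2.0227/√[(1+39r)/(1−r)]).

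- r = 0.01: (1.39/0.99) = 1.404, square root 1.185; 2.0227/1.185 = 1.707; rate 9.6%.
- r = 0.05: (2.95/0.95) = 3.105, square root 1.762; 2.0227/1.762 = 1.148; rate 26%.
- r = 0.10: (4.90/0.90) = 5.444, square root 2.333; 2.0227/2.333 = 0.867; rate 39%.

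A very small common component is therefore enough to break the 5% level.

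**The two definitions on the pilot data.** Assume that a 30% change means at least 30%, and that the nine increases are among the 19 significant hemispheres. All nine are then appropriate under the significance rule. At most six can reach a 30% increase, so at least 9 − 6 = 3 are also a lack of response under the 30% rule. If all six 30% changes were decreases (their direction is not given), the number is 9.

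**The case against.** The strongest reply is that the main aim does not use this p-value. Statistical Considerations and the end of IRB Concerns both aim to correlate CBF response with later vasospasm, and the former names percent change as the measure. The percent changes are not biased by the error. The study images do not guide care, and the document itself says no robust statistics were possible in the initial pilot. All of this stands, and it limits the consequences.

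The slice test is also described in the past tense, and the images said to outline the statistics are missing from the available copy. That is fair. But the planned pre/post comparison is stated in the future tense, the sentence after it makes significance the mark of an appropriate response, and the readable text describes no other significance test for that comparison.

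The size of the inflation is assumed, and pairing by location removes stable differences between slices. Correct: only the direction is firm. Nor does neighbour correlation alone readily explain the pilot. At 68% per hemisphere, with hemispheres treated as independent, 19 or more of 20 has a probability of about 20 × 0.684^19 × 0.316 + 0.684^20 = 0.005. Correlated hemispheres or a larger whole-scan shift would soften this, but some of the 19 results may well survive correction. The near-even split of 9 up and 10 down is compatible with the error and does not prove it.

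Finally, averaging over a hemisphere may dilute a local deficit. That is a real cost, although the pilot results are already reported by hemisphere.

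**Conclusion.** The concern holds and should be fixed. As described, the test keeps its 5% level only if slice differences within one scan pair are uncorrelated, and nothing in the readable text supports or adjusts for that. The false-positive rate is about 7.5% to 68% for assumed neighbour correlations of 0.1 to 0.9, and about 10% to 39% for a common correlation of 0.01 to 0.10. These are ranges under assumption and do not estimate the rate in this study.

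The pilot count of 19 of 20, the change-detection part of the reproducibility claim, and the significance-based definition of an appropriate response cannot be relied on at the stated level. It does not follow that the 19 results are false. The percent changes, the 30% criterion and the main correlation aim are unaffected.

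The two definitions of response also need reconciling: on the assumptions given, they disagree on 3 to 9 of the nine pilot hemispheres with an increase.

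**What to change.** 1. Stop using the slice-level p-value to call a hemisphere changed or an appropriate response.
2. Average the 40 slices to one percent CBF change per hemisphere.
3. Relate that value to later symptomatic vasospasm with the patient as the unit. Either use one pre-specified value per patient, or fit a mixed model of percent CBF change (two hemispheres per patient) on later symptomatic vasospasm with a patient random intercept. Report an estimate with a 95% confidence interval.
4. State one definition of response, reconciling the significance rule with the 30% rule before the expanded data are analysed.
5. Report the pilot hemispheres as percent changes, without the p<0.05 claim.
6. If a within-hemisphere interval is kept, use an autocorrelation-adjusted standard error. Say that it still leaves out scan-to-scan error, which one scan before and one after cannot estimate.

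The cost is revised analysis wording and some re-analysis of existing maps, with no new patients or scans. The 19 of 20 statement is dropped or becomes less favourable, and single hemispheres can no longer be called changed on a p-value.

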Appendix A:

Diabetic		
	Creatinine	eGFR
Iohexol	< 1.4	>45
Iodixanol	1.4 – 2.0	45 – 30
No IV Contrast	> 2.0	<30

Non-Diabetic		
	Creatinine	eGFR
Iohexol	< 1.8	>30
Iodixanol	1.8 – 3.0	30 – 15
No IV Contrast	> 3.0	<15

Appendix B:

Hunt and Hess Grading Scale

- Grade 1: Asymptomatic or mild headache
- Grade 2: Cranial nerve palsy or moderate to severe headache/nuchal rigidity
- Grade 3: Mild focal deficit, lethargy, or confusion
- Grade 4: Stupor and/or hemiparesis
- Grade 5: Deep coma, decerebrate posturing, moribund appearance

Appendix C:

<https://uconnect.wisc.edu/policies/clinical/uwhc-clinical/uwhc-wide/legal-affairs/417.policy>

